4. ANALYSIS POPULATIONS

Part A: Pharmacodynamic	Comprise of all subjects who have taken at least one dose of study medication and one valid EGG data. Data will be assessed and reviewed by the central reader before it is considered valid. The central reader will provide the valid data that will be used for the analyses.	Pharmacodynamic
All Subjects	All subjects with at least one dose of study medication.	Safety
Enrolled	All enrolled subjects.	Enrolled

NOTES :

- Please refer to [Appendix 5](#): List of Data Displays which details the population to be used for each displays being generated.

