9.1.3.1. Analysis Populations

For this exploratory study, the analysis set will include subjects who have valid data. Data will be assessed and reviewed by the central reader before it is considered valid. Additional details will be provided in the RAP.

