9.5.3. Listings

Listings					
No.	Population	IDSL / TST ID / Example Shell	Title	Programming Notes	Deliverable [Priority]
1.	All Subjects		Listing of Subjects with Inclusion/Exclusion Criteria Deviations		
2.	All Subjects		Listing of Reasons for Withdrawal from Study		
3.	All Subjects		Listing of Demographics and Baseline Characteristics		
4.	All Subjects		Listing of Race		
5.	All Subjects		Listing of Subjects by Site ID		
6.	All Subjects		Listing of Concomitant Medication by Generic Term		
7.	All Subjects		Listing of All Adverse Events		
8.	All Subjects		Listing of Hematology Laboratory Data		
9.	All Subjects		Listing of Chemistry Laboratory Data		
10.	All Subjects		Listing of Urinalysis Laboratory Data		
11.	All Subjects		Listing of Laboratory Data for Subjects with Any Value of Potential Clinical Concern		
12.	All Subjects		Listing of Liver Functions with Any Value of Potential Clinical Concern		
13.	All Subjects		Listing of Vital Signs		
14.	All Subjects		Listing of GCSI-DD		
15.	All Subjects		Listing of Exposure Data		
16.	Pharmacodynamic		Listing of all EGG endpoints.		
17.	Pharmacodynamic		Listing of Visual Analogue Scale (VAS) Scores (0-100mm scale)		

Listings					
No.	Population	IDSL / TST ID / Example Shell	Title	Programming Notes	Deliverable [Priority]
18.	Pharmacodynamic		Listing of Gastric Emptying 13C Excreted in Breath (kPCD1) Over Time by Treatment and Visit		
19.	Pharmacodynamic		Listing of Time to Half Gastric Emptying (GET1/2) by Visit		
20.	Pharmacodynamic		Listing of Volume of Water Ingested during EGG with Water Load Test		

CONFIDENTIAL
The GlaxoSmithKline group of companies

204879

Division	: Worldwide Development
Information Type	: Reporting and Analysis Plan (RAP)

Title	: Reporting and Analysis Plan for A Randomized, Open-label, Active-Controlled, Parallel-Group, Exploratory Study on the Effects of Repeated Doses of Albiglutide compared to Exenatide on Gastric Myoelectrical Activity and Gastric Emptying in Subjects with Type 2 Diabetes Mellitus
Compound Number	: GSK716155
Effective Date	: 23-June-2017

Description:

- The purpose of this RAP is to describe the planned analyses and output to be included in the Clinical Study Report for Protocol 204879.
- This RAP is intended to describe the exploratory endpoints for the study Part A only.

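### In the SAP copy with Listings 16 to 20, a dosed subject with no valid EGG is left out of the gastric-emptying, VAS and water-volume listings as well as the EGG listing

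*SAP*

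**What the plan says.** SAP Section 4 sets three populations: Enrolled, All Subjects (at least one dose), and Pharmacodynamic. The last is defined as "Comprise of all subjects who have taken at least one dose of study medication and one valid EGG data", and the section adds: "The central reader will provide the valid data that will be used for the analyses". For the population of each display it refers to Appendix 5, the "List of Data Displays which details the population to be used for each displays being generated".

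The SAP file holds two copies of the plan, and they differ in Appendix 5.

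- In one copy, Section 9.5.3 assigns the Pharmacodynamic population to Listing 16 (EGG), Listing 17 (VAS), Listing 18 ("Listing of Gastric Emptying 13C Excreted in Breath (kPCD1) Over Time by Treatment and Visit"), Listing 19 ("Listing of Time to Half Gastric Emptying (GET1/2) by Visit") and Listing 20 ("Listing of Volume of Water Ingested during EGG with Water Load Test").
- In the other copy, Section 9.5.1 gives the exploratory endpoints Listing 15 only, and Section 9.5.3 shows Listing 15 as the EGG listing.

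In both copies Section 7.2 promises a listing for every endpoint.

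Protocol Section 9.1.3.1 says for Part A that "the analysis set will include subjects who have valid data", after central-reader review, with details left to the RAP. It does not make EGG validity a condition for the other endpoints.

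**The concern.** The entry condition fits one listing and is applied to five. EGG validity is a judgement on an electrical recording. It carries no information on whether a breath test was valid, and it does not decide whether a symptom rating or a drunk volume was correctly recorded. A subject with two good breath tests and no acceptable EGG would have no gastric-emptying row in the report, and no other display in that copy would supply one.

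For VAS there is a side effect. Under Protocol Section 7.4.1, nausea, hunger, fullness, bloating and abdominal pain caused by the water load are captured by VAS and are not recorded as adverse events. For a subject outside the Pharmacodynamic population, those timed ratings would appear neither in Listing 17 nor in the adverse event listing. Tolerance of the water load on top of a GLP-1 receptor agonist was one of the questions Part A had to answer (Protocol Section 4.2).

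The study stopped early with a limited number enrolled, so each missing subject is a noticeable part of what can be reported.

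**Working it through.** **Does each endpoint depend on the EGG signal?** The plan states no figure to reproduce, so the main check is to set the definitions side by side.

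| Listing | Data | Source (Protocol) | Depends on a valid EGG trace? |
|---|---|---|---|
| 16 | EGG parameters | 7.3.1 | Yes |
| 17 | VAS scores | 7.3.1: subject's own rating before and 10, 20 and 30 min after water | No, but same session |
| 18, 19 | kPCD, half-emptying time | 7.3 and 7.3.2: breath samples, separate day, mass spectrometry at a central laboratory | No |
| 20 | Water volume | 7.3.1: amount drunk in the water load | No, but same session |

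**When is a subject lost?** Part A plans two EGGs and two breath tests per subject (Protocol Section 4.1.1). One valid EGG is enough to enter the population. The Day 1 EGG is recorded before the first dose (Protocol Section 7.1, Part A table, footnote 11). A dosed subject is lost only if both EGGs are rejected, or if the subject had a single EGG and that one was rejected.

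**How likely is that?** The documents give no rejection rate and no enrolled number, so this is illustration only. Assume n = 10 dosed subjects with two EGGs each, and let q be the chance that a given EGG is rejected.

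- Independent rejections: the chance that a subject is excluded is q². Expected exclusions are 10 × q², and the chance of at least one is 1 − (1 − q²)^10.
- Rejections that always occur together in a subject: the chance of exclusion is q. Expected exclusions are 10 × q, and the chance of at least one is 1 − (1 − q)^10.

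| q (assumed) | Independent: expected | Independent: at least one | Together: expected | Together: at least one |
|---|---|---|---|---|
| 5% | 0.025 | 2.5% | 0.5 | 40.1% |
| 10% | 0.1 | 9.6% | 1 | 65.1% |
| 20% | 0.4 | 33.5% | 2 | 89.3% |
| 30% | 0.9 | 61.1% | 3 | 97.2% |

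The result depends almost wholly on q and on whether poor signal recurs in the same subject, and the documents inform neither. With fewer subjects the chances fall. For n = 5 and q = 10% they are 1 − 0.99^5 = 4.9% and 1 − 0.9^5 = 41.0%, while each subject lost is a larger share of the data.

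**The case against.** Much of the case on the other side stands.

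- **Size.** A reader might infer that one excluded subject is 10% of the planned 10. The SAP synopsis defines those 10 evaluable subjects by a valid pre-dose and a valid post-dose EGG, so a subject with no valid EGG is not one of them. Protocol Section 9.1.2.2 also allowed replacement when the reader found data invalid, although early termination means replacement cannot be relied on.
- **Stopped tests.** A reader might infer that a subject who vomits during the Day 4 water load vanishes from the report. That does not follow. A valid Day 1 EGG keeps the subject in, and a stopped test still includes 15 minutes of tracing before water, so it is not necessarily invalid. Vomiting is not among the five symptoms exempt from adverse event recording, so it can appear in Listing 7. The GCSI-DD, which covers nausea and vomiting, is Listing 14. Both use All Subjects. What an excluded subject loses is the timed VAS scores, not all symptom data.
- **Relatedness.** VAS and water volume come from the EGG session, and VAS of nausea is paired with EGG parameters in one Part A endpoint. Only gastric emptying is wholly separate.
- **Protocol.** The protocol leaves the details of the analysis set to the RAP. An EGG condition is a poor choice, but the protocol does not forbid it.
- **Consequence.** Part A tests no hypothesis, and SAP Section 7.1 replaces analysis of the exploratory endpoints with listings. SAP Sections 6.1 and 6.5.1 also allow additional analyses after data review.

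None of this explains why a breath-test listing should depend on an EGG.

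**Conclusion.** The point holds as a free improvement, in one of the two SAP copies. Read as written, Section 4 with Listings 17 to 20 omits a dosed subject with no valid EGG from three endpoints whose data may be sound. The mismatch is complete for gastric emptying and partial for VAS and water volume.

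The size is unknown. It rests on a rejection rate, a within-subject correlation and an enrolled number that the documents do not give, and no exclusion is shown to have occurred. A reader might infer a biased estimate of the exenatide effect. The documents do not support that, because no estimate or test is produced for these endpoints. The harm is possible incomplete reporting in a very small sample.

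The copy that stops at Listing 15 has a wider gap: it lists none of these endpoints for anyone, against its own Section 7.2. The file does not show which copy is current.

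**What to change.** 1. In SAP Section 9.5.3, change the population for Listings 17 to 20 to dosed subjects with a valid result for that test. Simply switching to All Subjects would drop the protocol's requirement that data be valid, so keep a validity condition specific to each test: the central laboratory result for the breath test, and a recorded rating or volume for VAS and water.
2. Add a column to these listings showing whether the subject's EGG at each visit was judged valid, so that readers can see which sessions had no acceptable trace.
3. Keep the EGG-based Pharmacodynamic population for Listing 16.
4. State which SAP copy is current. If it is the one ending at Listing 15, add listings for VAS, gastric emptying and water volume on the populations in item 1.

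In the copy with Listings 16 to 20 the cost is four population labels, one flag and a sentence on validity for each test. The other copy needs four added listings. No new data are needed. The SAP was prepared after the study had been terminated, so the sponsor can check the small data set directly for any dosed subject without a valid EGG.

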5.4. Screening/Randomization Failures

Screen failures are defined as subjects who consent to participate in the clinical trial but are never subsequently randomized. In order to ensure transparent reporting of screen failure subjects, meet the Consolidated Standards of Reporting Trials (CONSORT) publishing requirements, and respond to queries from Regulatory authorities, a minimal set of screen failure information is required including Demography, Screen Failure details, Eligibility Criteria, and Serious Adverse Events (see Section 7.4.1.6).

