7.4.1.1. Time period and Frequency for collecting AE and SAE information

- Any SAEs assessed as related to study participation (e.g., protocol-mandated procedures, invasive tests, or change in existing therapy) or related to a GSK product will be recorded from the time a subject consents to participate in the study up to and including any follow-up contact.
- AEs will be collected from the start of Study Treatment until the follow-up contact (see Section 7.4.1.3), at the timepoints specified in the Time and Events Table (Section 7.1).
- Medical occurrences that begin prior to the start of study treatment but after obtaining informed consent may be recorded on the Medical History/Current Medical Conditions section of the eCRF.
- All SAEs will be recorded and reported to GSK within 24 hours, as indicated in [Appendix 6](#).
- Investigators are not obligated to actively seek AEs or SAEs in former study subjects. However, if the investigator learns of any SAE, including a death, at any time after a subject has been discharged from the study, and he/she considers the event reasonably related to the study treatment or study participation, the investigator must promptly notify GSK.

NOTE: The method of recording, evaluating and assessing causality of AEs and SAEs plus procedures for completing and transmitting SAE reports to GSK are provided in [Appendix 6](#).

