6.5. Safety Analyses

6.5.1. Overview of Planned Analyses

The safety analyses will be based on all subjects' population.

Table 3 provides an overview of the planned analyses, with further details of data displays being presented in [Appendix 5: List of Data Displays](#).

Table 3 Overview of Planned Safety Analyses

Endpoints	Observed				Change from Baseline			
	Summary		Individual		Summary		Individual	
	T	F	F	L	T	F	F	L
Adverse Events	Y			Y				
Clinical Laboratory				Y				
Vital Signs				Y				
GCSI-DD				Y				

NOTES :

- T = Table, F = Figure, L = Listing, Y = Yes display generated.
- Stats Analysis = Represents TFL related to any formal statistical analyses (i.e. modelling) conducted.
- Summary = Represents TFL related to any summaries (i.e. descriptive statistics) of the observed raw data.
- Individual = Represents FL related to any displays of individual subject observed raw data.

Following review of the data, additional analyses maybe conducted to further support the evaluation and interpretation of the data.

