9.5.2. Study Population Tables

Study Population Tables					
No.	Population	IDSL / TST ID / Example Shell	Title	Programming Notes	Deliverable [Priority]
[Disposition]					
1.1.	All Subjects	ES1/ES1A	Summary of Subjects Disposition for the Subject Conclusion Record		
[Demographics and Baseline Characteristics]					
1.2.	All Subjects	DM1	Summary of Demographic Characteristics		
1.3.	All Subjects	DM5	Summary of Race & Racial Combinations		
1.4.	Enrolled	NS1	Summary of Number of Subjects by Country and Site ID		
1.5.	Enrolled	DM11	Summary of Age Ranges		
Safety Tables					
1.6.	All Subjects	AE15	Summary of Common (>=2%) Non-serious AEs by System Organ Class and Preferred Term		
1.7.	All Subjects	AE16	Summary of Serious AEs by System Organ Class and Preferred Term		

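### SAEs that the protocol records from consent appear in no SAP table or listing if the subject is never dosed

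*SAP*

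**What the plan says.** **Populations.** SAP section 4 defines All Subjects, which it labels Safety, as "All subjects with at least one dose of study medication". Enrolled is "All enrolled subjects", with no statement of when a subject counts as enrolled. The Pharmacodynamic set also requires a dose. Section 4 leaves the population for each display to Appendix 5, and section 6.5.1 states: "The safety analyses will be based on all subjects' population".

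**Displays.** Appendix 5 assigns All Subjects to Table 1.1 ("Summary of Subjects Disposition for the Subject Conclusion Record"), Table 1.7 ("Summary of Serious AEs by System Organ Class and Preferred Term"), Listing 2 (reasons for withdrawal) and Listing 7 ("Listing of All Adverse Events"). Enrolled is used only for Tables 1.4 (site counts) and 1.5 (age ranges). The SAP file contains the plan twice, and both copies assign these populations in the same way. Section 6.5.2 says, without restriction, that every AE will be listed by subject.

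**Collection.** Under protocol 7.4.1.1, SAEs judged related to study participation (procedures, tests or a change in existing therapy) or to a sponsor product "will be recorded from the time a subject consents to participate in the study up to and including any follow-up contact". Non-serious AEs are collected only once treatment starts. For screen failures, protocol 5.4 says that "a minimal set of screen failure information is required including Demography, Screen Failure details, Eligibility Criteria, and Serious Adverse Events", and gives transparent reporting as one of the reasons.

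**The concern.** The protocol begins collecting participation-related SAEs at consent because subjects are exposed to study procedures before they receive any drug. The SAP then reports SAEs only for people who reached the first dose. A serious event during washout or at a baseline test is a plausible reason for not going on to dosing, so the filter may remove subjects for a reason connected with the event itself. The same filter governs disposition and withdrawals, so those displays would not show that the subject is missing.

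At stake is the completeness of the safety section of the study report. It could show no SAEs while the safety database holds one attributed to a study procedure. Appendix 2 of the protocol names nausea or vomiting during the water load as a risk that may need medical care, and says that no published incidence data exist. In a study stopped early with few subjects, a single omitted event would be a material omission.

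**Working it through.** The plan states no figure that bears on this point, so the check is a trace through the documents.

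**Step 1. Population of each relevant display (SAP section 4 and Appendix 5)**

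| Display | Content | Population |
|---|---|---|
| Table 1.1 | Disposition | All Subjects (dosed) |
| Table 1.7 | Serious AEs | All Subjects (dosed) |
| Listing 2 | Reasons for withdrawal | All Subjects (dosed) |
| Listing 7 | All AEs | All Subjects (dosed) |
| Tables 1.4, 1.5 | Site counts, age ranges | Enrolled |

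Of the displays that carry SAEs, disposition or withdrawals, 4 of 4 are limited to dosed subjects and 0 of 4 use a wider set. The two Enrolled tables hold no event data.

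**Step 2. What precedes the first dose in Part A**

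- OAM washout: 2 days (immediate release) or 4 days (extended release) before baseline (protocol 4.1.1).
- Baseline breath test: Day -1 (protocol Table 2).
- Baseline EGG with water load: Day 1, with the first exenatide dose given afterwards (protocol Table 2, footnote 11).

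All three follow consent, so a related SAE at any of them falls within the collection rule of protocol 7.4.1.1.

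**Step 3. Where such an SAE is shown**

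| Subject | Meets the All Subjects definition? | SAE in Table 1.7 and Listing 7? |
|---|---|---|
| Pre-dose SAE, later dosed | Yes | Yes; SAP 5.1 assigns it to the pre-dose period |
| Pre-dose SAE, never dosed | No | No; the subject is also absent from Table 1.1 and Listing 2 |
| SAE after first dose | Yes | Yes |

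Only the middle row is lost. The filter acts on people, not on dates.

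**Step 4. Size**

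A rate would need the number of consented subjects who were never dosed and the number of those with a related SAE. The documents give neither, so no percentage is calculated. For each such event the planned displays show 0 where the database holds 1.

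**The case against.** The strongest reply is that a dosed safety set is conventional, and that this SAP is openly cut down: section 2.1 says early termination leaves only listings of selected data. SAEs go to the sponsor within 24 hours whatever the SAP displays, and protocol 7.4.1.6 covers onward reporting to regulators, ethics committees and investigators. Protocol 5.4 requires screen-failure information to be available but does not place it in a particular table, and its definition of a screen failure turns on randomization, which Part A does not have. Section 6.5.2 can be read as subject to 6.5.1. The SAP also allows further analyses after data review.

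The case is narrow too. Before dosing, only SAEs related to participation or a sponsor product are collected. Nausea, hunger, fullness, bloating and abdominal pain caused by the water load are VAS endpoints, not AEs (protocol 7.4.1). No passage says that a subject with a pre-dose SAE would go undosed; that is inference.

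Most of this stands, and it limits the point. It justifies the dosed set for rates. It does not explain why events deliberately collected from consent have no display at all. Expedited reporting does not replace the study report, the option of further analyses commits to nothing, and section 2.1 does not say that SAEs in undosed subjects are dropped on purpose.

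**Conclusion.** The gap is real and narrow. As written, the SAP shows a participation-related SAE in a never-dosed subject in none of its tables or listings, which does not match the unrestricted promise in section 6.5.2 or the collection rules in protocol 7.4.1.1 and 5.4. The conclusion rests on applying the Appendix 5 population column literally. Its practical effect depends on whether any such event occurred, which the documents do not report.

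A reader might infer more than the documents support:

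- **That all SAEs between consent and first dose are excluded.** They are not; those in subjects later dosed are retained.
- **That one omitted event moves the SAE rate from 0 to 1 in 10.** The planned 10 are evaluable subjects, whom the SAP synopsis defines as having valid pre-dose and post-dose EGGs. A never-dosed subject cannot be one of them.
- **That the decision to start Part B is compromised.** The criterion in protocol 4.2 concerns the water load added to a GLP-1 receptor agonist, so it is informed by dosed subjects. The study had also terminated by the time the SAP was prepared.
- **That the event would be lost altogether.** It would be in the database and reported to the sponsor.

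**What to change.** 1. Keep the dosed All Subjects set for Tables 1.6 and 1.7 and for any on-treatment rate.
2. Run the SAE part of Listing 7, or one added SAE listing, on all consented subjects. Flag pre-dose events using the SAP 5.1 rule, and flag subjects who were never dosed. Align sections 6.5.1 and 6.5.2 with this.
3. Add to disposition a count, with reasons, of subjects who consented but were not dosed. Keep it separate from withdrawals, so that ordinary screen failures do not enter Listing 2.
4. Define the consented population in section 4. Enrolled should not serve here: it is undefined, and the Part A schedule places enrolment into the treatment phase on Day 1, so a subject lost during washout or after the Day -1 breath test could still fall outside it.

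The cost is one population definition, one listing and one count line, with a few screen-failure records included. No new data are needed, because the protocol already requires both the SAEs and the screen-failure details to be collected.

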5. CONSIDERATIONS FOR DATA ANALYSES AND DATA HANDLING CONVENTIONS

5.1. Reporting Conventions

- All data displays will be presented according to the Integrated Data Standards Library (IDSL) reporting standards, where applicable.
- Analyses will be performed using the 9.1.3 version of the SAS System or higher (SAS is a registered trademark of the SAS Institute Inc., Cary, NC, USA). Programs will be imported into HARP and the final output will be produced by running drivers in HARP.
- Data collected at unplanned (i.e. unscheduled) time points will not be included in the summaries by visit unless otherwise stated. Unscheduled or unplanned readings will be presented in the listings and they will be included when determining worst-case flagging for post-baseline summaries.
- In all data displays, planned and actual relative times will be relative to the study drug dosing time of the relevant dosing session.
- Refer to IDSL standards (when applicable) for decimal place conventions. Raw data will generally be presented to the same number of decimal places as it was collected.
- All data will be reported according to the actual treatment the subject received. Any departures from the planned treatment according to the randomization schedule will be documented in the report.
- All observations that occurred prior to dosing will be considered as part of the pre-dose period. All observations that occur during dosing will be attributed to the subject's treatment.

Deviations from the analyses in the RAP will be identified in the final clinical study report.

[Table 1](#) provides an overview of appendices within the RAP for outlining general considerations for data analyses and data handling conventions.

Table 1 Overview of Appendices

Section	Component
9.1	Appendix 1 : Time & Events
9.2	Appendix 2 : Assessment Windows
9.3	Appendix 3 : Values of Potential Clinical Importance
9.4	Appendix 4 : Abbreviations and Trademarks
9.5	Appendix 5 : List of Data Displays

